Title: Ubiquinol as a Metabolic Resuscitator in Post-Cardiac Arrest

Date: 12/20/2020

NCT: NCT02934555

Study overview: A single-center, prospective, double-blind, randomized, placebo-controlled phase II trial comparing oral liquid coenzyme Q10 to placebo after cardiac arrest. Consecutive adult patients who present with the following inclusion criteria and meeting none of the exclusion criteria will be approached for consent.

Inclusion criteria:

Adult (age \geq 18 years)
Cardiac arrest (in- or out-of-hospital)
Not following commands after ROSC
Ability to receive enteral medication

Exclusion criteria:

Protected populations
Current coenzyme Q10 supplementation
Anticipated death within 24 hours
> 12 hours from ROSC to randomization

Consent: The legally authorized surrogate of patients who meet all inclusion criteria and no exclusion criteria will be approached for written informed consent by members of the investigative team per standard procedures and approval from the Institutional Review Board. The study will be performed according to the Helsinki declaration.

Randomization and blinding: We will create a master randomization list stratified by the presence of shock at the time of randomization (shock defined as use of vasopressors). Patients, clinicians, and the research team will remain blinded throughout the full duration of the study.

Treatment protocol: Upon enrollment, demographic data including age, sex, race, and ethnicity, as well as vital signs and laboratory data will be recorded. A research assistant will perform venipuncture and the blood will be centrifuged and aliquoted into light-protected cryotubes and frozen at minus 80°C. After randomization and the initial blood draw, patients will be administered the study drug or placebo and will receive two daily dosages for 7 days, until hospital discharge, or until normal neurological function. Subsequent blood draws and clinical information will be collected at 24, 48 and 72 hours after the initial draw. Patients will be followed to hospital discharge for clinical outcomes.

Dosage regimen: For dose, we will be providing 300 mg of ubiquinol (active coenzyme Q10) every 12 hours. Any adverse events will be reported in real-time to the Institutional Review Board.

Outcomes: The primary outcome will be coenzyme Q10 plasma levels. Secondary outcomes will include additional biomarker measurements (including neuron specific enolase), oxygen consumption, and clinical outcomes (mortality and neurological outcomes).

Statistical analysis plan: Descriptive statistics will be used to summarize the study population. Our primary time-point of interest will be 24 hours after administration of the study drug. As a secondary analysis, we will use repeated measures linear models to analyze differences in outcomes over all time-points (0, 24, 48, and 72 hours). An appropriate variance-covariance structure will be chosen based on the Akaike Information Criteria. Right-skewed variables will be log-transformed before these analyses. All hypothesis tests will be two-sided and a p-value < 0.05 will be considered significant.

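### Randomisation is stratified by vasopressor use, but the analysis plan never uses the stratum, so it cannot show whether an enteral drug raises plasma CoQ10 in patients in shock

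*Combined protocol and SAP*

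**What the plan says.** Under Randomization and blinding, the master list is "stratified by the presence of shock at the time of randomization (shock defined as use of vasopressors"). No other stratification factor is named.

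The drug goes in by the enteral route. The inclusion criteria ask for "Ability to receive enteral medication", which concerns whether a dose can be given, not how much is taken up. Under Dosage regimen, "we will be providing 300 mg of ubiquinol (active coenzyme Q10) every 12 hours", with no distinction by stratum.

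Under Outcomes, "The primary outcome will be coenzyme Q10 plasma levels". Under Statistical analysis plan, "Our primary time-point of interest will be 24 hours after administration of the study drug", and as a secondary analysis "we will use repeated measures linear models to analyze differences in outcomes over all time-points (0, 24, 48, and 72 hours"). The section closes with "All hypothesis tests will be two-sided and a p-value < 0.05 will be considered significant".

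The analysis plan names no test or model for the 24-hour comparison. It does not mention shock or vasopressors, either as a model term or as a basis for separate estimates. Sample size, expected effect, standard deviation, allocation ratio and expected share of patients in shock are not stated.

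**The concern.** The primary endpoint is in effect a question about exposure: does an enteral dose reach plasma? Anything that limits uptake acts on the active arm only, because placebo patients have no study dose to absorb. If uptake differs by vasopressor use, shock modifies the treatment effect, beyond any role it has as a prognostic factor. A single overall difference then averages two different effects.

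The average can mislead in either direction. A significant overall difference may come mainly from patients not on vasopressors. A non-significant one may hide good uptake in those same patients. A null result on the secondary biomarkers is also harder to read if it is not known whether the drug reached plasma in both groups.

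The stratum is the trial's own, is recorded at randomisation, and should be roughly balanced between arms by design. If no stratum estimates are specified in advance, any later statement about patients on vasopressors will be a post hoc subgroup finding.

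**Working it through.** **Nothing to reproduce.** The plan states no sample size, power or effect size. The figures below illustrate the mechanism on assumed inputs.

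**Inputs.** From the documents: two strata, and two-sided alpha 0.05. Assumed: 1:1 allocation; n = 30 per arm in the central case; outcome SD = 1 within stratum and arm (log scale if skewed); effect d = 1.5 SD without shock; effect 0 with shock, as the extreme case; shock share s = 50%, varied from 30% to 70%.

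**Overall difference.** With no effect in shock it is (1 − s)d. Central case: 0.5 × 1.5 = 0.75 SD.

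**Power of the overall test.**
- Normal approximation: SE = √(2/30) = 0.258; 0.75/0.258 = 2.90; power = Φ(2.90 − 1.96) = 0.83.
- This ignores the extra spread that a mixture of effects creates in the active arm. A simulated two-sample t-test allows for it (4,000 trials per setting, 30 per arm, d = 1.5):

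| Shock share | Overall t-test | Adjusted for stratum | Interaction test |
|---|---|---|---|
| 30% | 0.97 | 0.97 | 0.76 |
| 50% | 0.72 | 0.76 | 0.82 |
| 70% | 0.33 | 0.36 | 0.73 |

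The test within the shock stratum rejects in about 5% of trials throughout, as it should when there is no effect there. Adjusting for the stratum gains a little power but still gives one averaged difference. Only stratum estimates or an interaction term separate the two groups.

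**Precision of a stratum estimate.** With 15 per arm in a stratum, the half-width of the 95% CI is t(0.975, 28) × √(2/15) = 2.048 × 0.365 = 0.75 SD.

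**Precision of the interaction.** The difference between the two stratum effects has SE = √(4/15) = 0.516.
- No effect in shock: 1.5/0.516 = 2.90, so power is about 0.83 by normal approximation (0.82 simulated).
- Half the effect in shock (0.75 SD): the stratum effects differ by 0.75; 0.75/0.516 = 1.45; power = Φ(1.45 − 1.96) = Φ(−0.51), about 0.30.

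A partial reduction in uptake would therefore usually not give a significant interaction. This is why the output should be estimates with intervals.

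**Why a consistency rule would not work.** One might extend the overall result to patients on vasopressors whenever the shock-stratum 95% CI contains the overall estimate. In the central case the shock-stratum half-width (0.75) equals the expected overall difference (0.75), so the rule has little power to object. In simulation with no effect in shock, and among trials with a significant overall result, it would wrongly extend the claim in about 49% with half in shock and about 83% with 70% in shock (30 per arm, d = 1.5).

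**The case against.** Four points can be made for the plan.

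1. **The analysis plan does not commit to an unstratified comparison.** It names no primary test, so a stratified or adjusted analysis is neither specified nor excluded. This stands, and a reader should not say that the plan reports one pooled contrast. The silence does not fill the gap, however: nothing in the plan provides a result by stratum.

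2. **The documents say nothing about uptake on vasopressors.** They give no reason for the stratification, which may simply balance severity. This stands. A reader might infer that patients on vasopressors absorb nothing; the documents do not support that. Zero uptake is used above only as the extreme case. What can be said is that uptake may differ, because the drug is enteral and the endpoint is its plasma level.

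3. **An average over all randomised patients is a valid phase II comparison.** This stands. In the scenario above the average effect is truly nonzero, so a significant overall test is not a false positive.

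4. **The documents do not say to whom a positive result would be applied.** A reader might infer that it would be claimed for patients on vasopressors. That is a risk in reading the result, not something the plan states.

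It is also fair to say that leaving the 24-hour test unnamed is the more basic omission. The fix below therefore states how the stratum enters that comparison as well as asking for estimates by stratum.

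**Conclusion.** The point holds as a gap in interpretation. The trial randomises by vasopressor use and the analysis plan then makes no use of it, so as written the plan cannot show whether plasma CoQ10 rises in patients in shock. The overall comparison remains valid and type I error is unaffected.

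The size depends entirely on assumed inputs. With 30 per arm, 1.5 SD without shock and no effect in shock, the overall test is significant in about 97%, 72% and 33% of trials as the shock share goes from 30% to 50% to 70%. An overall result carried by one stratum is therefore possible, but less likely as more patients are in shock; at a high shock share the larger risk is missing real uptake in the others. If uptake is reduced only in part, the contrast between strata is smaller and harder to detect.

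The stronger reading, that a positive result would be wrongly claimed for patients who absorb nothing, goes beyond the documents.

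**What to change.** Add to the statistical analysis plan wording such as:

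*The primary analysis is the overall active-versus-placebo comparison of CoQ10 at 24 hours (log scale if skewed), from a model that includes the shock randomisation stratum. The active-minus-placebo difference with 95% CI will also be reported in each stratum, together with the treatment-by-stratum interaction estimate and its 95% CI. These are descriptive estimates and not additional confirmatory tests.*

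Do not add a rule that extends the overall result to patients on vasopressors when the shock-stratum estimate is merely consistent with it. A wide interval would then count as evidence of effect.

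The cost is wording only. The stratum is recorded at randomisation and the 24-hour sample is already scheduled, so no new data are needed. The small downside is imprecision: a half-width of about 0.75 SD with 15 per arm per stratum (an assumed size), and interaction power of about 30% if the effect in shock is half of 1.5 SD with 30 per arm and 50% in shock. The report should say so next to the estimates.

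### Does the primary 24-hour time-point miss the sampling schedule because one is counted from the dose and the other from the baseline draw?

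*Combined protocol and SAP*

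**What the plan says.** The Outcomes section makes the endpoint a concentration: "The primary outcome will be coenzyme Q10 plasma levels". The Statistical analysis plan then sets the time: "Our primary time-point of interest will be 24 hours after administration of the study drug". The sentence after that describes a secondary repeated-measures analysis of "differences in outcomes over all time-points (0, 24, 48, and 72 hours").

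The only sampling schedule is in the Treatment protocol: "Subsequent blood draws and clinical information will be collected at 24, 48 and 72 hours after the initial draw". The same section puts the baseline sample before treatment: "After randomization and the initial blood draw, patients will be administered the study drug or placebo". It describes dosing as "will receive two daily dosages for 7 days, until hospital discharge, or until normal neurological function", and the Dosage regimen adds "we will be providing 300 mg of ubiquinol (active coenzyme Q10) every 12 hours".

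None of these sections bounds the delay from baseline draw to first dose, gives a window for the 24-hour draw, or states the order of that draw and the dose due at about the same time.

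**The concern.** The two sections count 24 hours from different events. Because the baseline draw comes first, the clocks agree only if the delay to the first dose is zero. Otherwise the primary time-point, taken literally, has no sample.

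For many endpoints this would not matter. Here the endpoint is the plasma level of the substance being given, so the number of doses received and the time since the last one determine what exposure the primary result describes. Doses are 12 hours apart, so a third dose falls due 24 hours after the first, close to the primary sample. If some patients were sampled before that dose and others after it, the active-arm result would mix two kinds of level, with extra scatter and a less clear meaning. If actual times were not recorded, the order could not be reconstructed.

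**Working it through.** There is no stated figure to reproduce: the plan gives no sample size, power or pharmacokinetic values. The check is a timeline.

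**Inputs**
- Baseline draw before the first dose; later draws counted from the baseline draw (Treatment protocol).
- Doses 12 hours apart (Dosage regimen).
- L, hours from baseline draw to first dose: not given. I use 0.25 to 6 hours for illustration only.
- W, half-width of the sampling window in hours: not given. I use ±1, ±2 and ±4 for illustration only.

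**Formulas.** Put the baseline draw at time 0. Doses fall at L, L + 12 and L + 24. The scheduled draw at 24 is therefore
- 24 − L hours after dose 1,
- 24 − (L + 12) = 12 − L hours after dose 2,
- (L + 24) − 24 = L hours before dose 3.

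| Assumed L (h) | After dose 1 (h) | After dose 2 (h) | Before dose 3 (h) |
|---|---|---|---|
| 0.25 | 23.75 | 11.75 | 0.25 |
| 1 | 23 | 11 | 1 |
| 2 | 22 | 10 | 2 |
| 6 | 18 | 6 | 6 |

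**Which sample is meant?** On the dose clock the baseline sample sits at −L and the later samples at 24 − L, 48 − L and 72 − L. On the draw clock they sit at 0, 24, 48 and 72, which is the list in the analysis plan. Only the draw clock reproduces that list, and only one draw lies near 24 hours.

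**When could the order go wrong?** The draw follows dose 3 only if relative timing slips by more than L.
- L = 0.25, W = 1: the draw can fall between 23 and 25. The early limit is 23 − 12.25 = 10.75 h after dose 2; the late limit is 25 − 24.25 = 0.75 h after dose 3.
- L = 1, W = 2: from 22 − 13 = 9 h after dose 2 to 26 − 25 = 1 h after dose 3.
- L = 2, W = 2: from 22 − 14 = 8 h to 26 − 14 = 12 h after dose 2, so not past dose 3.
- L = 2, W = 4: from 20 − 14 = 6 h after dose 2 to 28 − 26 = 2 h after dose 3.

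The two worries therefore work against each other. A large L makes the clocks disagree but protects the order of sample and dose. A small L leaves the order open to slippage but makes the disagreement trivial (15 minutes in 24 hours at L = 0.25).

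**Would a single clock change the data?** Counting everything from the draw changes only the wording: L still varies between patients, and so does time since dose. Counting everything from the first dose puts the sample at L + 24, exactly when dose 3 is due, so the order of sample and dose becomes more delicate. Neither choice removes the source of scatter without some cost.

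**The case for a change.** The strongest case for acting is that this is the primary endpoint, the conflict is explicit, and clarification would be cheap. L cannot simply be taken as small: nothing bounds it, and it may include dose preparation and enteral delivery. Whatever L is, the window and the order of sample and dose at 24 hours are unstated, and with a short L and a ±1 hour window the sample could follow either two doses or three. A reader cannot tell from the plan alone whether the primary result is always a pre-dose level.

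That much stands as a description of missing detail. It does not establish a consequence. The nominal schedule places the draw before dose 3 for every positive L. The two descriptions of dosing frequency are compatible, the 12-hourly one being more specific, so they do not show that doses would drift. Across the assumed L values, time since dose 2 ranges over 11.75 − 6 = 5.75 hours, but this only compares the ends of a range I chose and does not estimate variation between patients. The documents give no absorption or half-life data, so no difference in level can be claimed. Whether dose and draw times are recorded is not stated either way, so a loss of that information is a possibility, not a finding.

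**Conclusion.** The wording differs between the two sections, but no change to the plan is needed. The phrase in the analysis plan is best read as loose wording for the scheduled 24-hour draw. That draw is the only candidate, and the list of times in the next sentence confirms it, so analysts would fill the gap in the same way.

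The mismatch equals L, which is unknown: 0.25 hours if dosing is prompt, 2 hours if it is slower, both assumed. It does not bias the comparison, because both blinded arms follow the same schedule and the choice of draw does not depend on assignment. What remains is possible extra scatter in the active arm, of a size the documents do not allow one to calculate, and some looseness about how close to a dose the sample was taken. No result or conclusion is shown to depend on either.

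This rests on three assumptions: doses are held close to 12 hours apart, the draw is taken near its scheduled time, and the primary analysis uses the scheduled 24-hour sample.

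### The secondary repeated-measures analysis does not state that the pre-dose 0 h value serves as a baseline adjustment; stating it would cost nothing and could improve precision

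*Combined protocol and SAP*

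**What the plan says.** The Treatment protocol section fixes the order of events: "After randomization and the initial blood draw, patients will be administered the study drug or placebo". It counts the later samples from that same draw: "Subsequent blood draws and clinical information will be collected at 24, 48 and 72 hours after the initial draw". The 0 h value is therefore measured before treatment in both arms.

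The Statistical analysis plan section names 24 h as the primary time-point ("Our primary time-point of interest will be 24 hours after administration of the study drug"). As a secondary analysis it proposes "repeated measures linear models to analyze differences in outcomes over all time-points (0, 24, 48, and 72 hours". Two further details are given. The first is "An appropriate variance-covariance structure will be chosen based on the Akaike Information Criteria"; the second is "Right-skewed variables will be log-transformed before these analyses".

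The section lists no model terms. It mentions neither a baseline covariate, nor a common 0 h mean, nor change from 0 h.

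**The concern.** A pre-dose measurement cannot carry a treatment effect, so any difference between arms at 0 h is chance. Its use in a randomized comparison is to explain between-patient variation in the later values. The secondary analysis places 0 h alongside the three post-dose times and does not say whether it plays that role.

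What is at stake is precision. Two familiar models that fit the sentence, arm-by-time with free 0 h means and change from 0 h, can leave the arm comparison less precise than the data allow. The blood has already been drawn and assayed, so nothing is saved by leaving the adjustment out.

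**Working it through.** The documents state no SD, correlation, sample size, allocation ratio or effect size, so there is no figure of the plan's to reproduce. Everything below is illustrative.

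**Inputs**
- From the documents: 0 h is pre-dose; post-dose visits are at 24, 48 and 72 h.
- Assumed: 1:1 allocation with n per arm; r is the correlation of the 0 h and 24 h values on the analysed scale; SD = 1 at both times in both arms; complete data.

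**Variance of the arm difference at 24 h**
- Raw: 2/n. With complete data and free arm-by-time means, the repeated-measures model returns exactly this contrast, whichever covariance structure is selected.
- Change from 0 h: 2 × 2(1 − r)/n.
- Adjusted for 0 h: 2(1 − r²)/n.

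So raw ÷ adjusted = 1/(1 − r²), and change ÷ adjusted = 2(1 − r)/(1 − r²) = 2/(1 + r).

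**Variance of the 24–72 h average**, assuming the same correlation r between every pair of visits: unadjusted (1 + 2r)/3 and adjusted (1 + 2r)/3 − r², each times 2/n. At r = 0.5 this gives 0.667/0.417 = 1.60.

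| Assumed r | Raw ÷ adjusted, 24 h | Change ÷ adjusted, 24 h | Raw ÷ adjusted, 24–72 h mean |
|---|---|---|---|
| 0.1 | 1.01 | 1.82 | 1.03 |
| 0.2 | 1.04 | 1.67 | 1.09 |
| 0.3 | 1.10 | 1.54 | 1.20 |
| 0.5 | 1.33 | 1.33 | 1.60 |
| 0.7 | 1.96 | 1.18 | 2.58 |

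A simulation of the 24 h contrasts (20,000 trials, an assumed 100 per arm, true effect 0.5) gave raw ÷ adjusted of 1.09, 1.31 and 1.93 at r = 0.3, 0.5 and 0.7, close to the formula. All contrasts averaged 0.50, so none is biased.

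**Sensitivity 1: missing 24 h values.** Let a fraction f be missing completely at random, with 0 h complete. An ordinary arm-by-time likelihood fit then recovers some of the loss. Its ratio to the common-0 h-mean model is 1 + (1 − f)r²/(1 − r²). At r = 0.3, 0.5 and 0.7 this is 1.08, 1.27 and 1.77 for f = 0.2, and 1.06, 1.20 and 1.58 for f = 0.4.

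**Sensitivity 2: arms that differ.** Let the 24 h SD be 1 on placebo and 2 on treatment, with 0 h SD 1 in both. The pooled slope b is the mean of r × SD over the arms, and the ratio is Σ SD² ÷ Σ(SD² − 2b·r·SD + b²).
- Same r = 0.5 in both arms: b = 0.75; 5/(5 − 4.5 × 0.25) = 5/3.875 = 1.29.
- Placebo r = 0.5, treated r = 0: b = 0.25; the placebo term is 1 − 0.25 + 0.0625 = 0.8125, the treated term is 4 + 0.0625 = 4.0625, and 5/4.875 = 1.03.

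**Sensitivity 3: small trial.** Estimating the slope inflates the adjusted variance by about 1 + 1/(2n − 4). At an assumed 10 per arm this is 1 + 1/16 = 1.06. The 24 h gain at r = 0.3 then falls from 1.10 to about 1.03. At r = 0.1 or 0.2 it disappears (1.01/1.06 and 1.04/1.06 are both below 1).

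**The case against.** The strongest reply is that the plan is silent on this point and not wrong. A repeated-measures model with 0 h in the outcome vector and a common 0 h mean fits the quoted sentence and loses nothing. A reader might infer that the plan discards the baseline; the text does not say so. This part of the reply stands, which is why the point is limited to what is left unstated.

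The second reply is that the gain may be small. The primary outcome is the blood level of the substance being given ("The primary outcome will be coenzyme Q10 plasma levels"). Dosing could therefore weaken the link between 0 h and 24 h in the treated arm, and low correlations or small numbers shrink the benefit further. This also stands: the sensitivity cases reach 1.03 and, at very low correlation in a very small trial, no gain at all. It bears on the size of the gain; it gives no reason to leave the handling of 0 h unstated.

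The third reply is that a likelihood fit already makes use of 0 h. That is only partly true. It recovers some precision when post-dose values are missing. With complete data and free 0 h means it returns the raw visit contrast.

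The last reply is that this is a matter of preference in a secondary analysis. It is fair as to priority: an unadjusted randomized comparison is valid, and including 0 h as an outcome is not an error.

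**Conclusion.** The point holds in a narrow form. The secondary analysis does not state that the pre-dose 0 h value is used as a baseline adjustment. If it is not so used, the 24 h contrast has between 1.01 and 1.96 times the necessary variance over assumed correlations of 0.1 to 0.7, given complete data, equal SDs, equal correlations and numbers large enough to ignore slope estimation. Change from 0 h has 1.82 to 1.18 times over the same range. The true size is unknown, because the documents supply none of the inputs, and it could be close to nil for coenzyme Q10 itself.

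Two stronger conclusions might be drawn, and the documents support neither.
- **A diluted treatment effect.** If a single arm effect were averaged equally over all four times, it would estimate (0 + d24 + d48 + d72)/4. That is 0.75 of the post-dose average (d24 + d48 + d72)/3, whatever the shape of the effect. The plan does not adopt that contrast. Its sentence reads at least as naturally as differences by visit, where this dilution does not arise. A single-effect fit under a selected covariance structure need not weight the visits equally either.
- **Harm to the primary comparison or to validity.** The 24 h primary time-point is separate from this model and is not diluted by 0 h. Raw and change contrasts are unbiased under randomization.

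Priority is low: a free improvement that could be made, not a defect that must be repaired.

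**What to change.** Add two or three sentences to the Statistical analysis plan section, choosing one of these:
- Model the 24, 48 and 72 h values with arm, time, arm-by-time, the 0 h value and its interaction with time. Log the 0 h value whenever the outcome is logged.
- Keep 0 h in the outcome vector and constrain the arms to a common 0 h mean.

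In either case, base the arm comparison on the post-dose visits: report the difference at 24, 48 and 72 h and the 24–72 h average, and say which of these is tested.

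The cost is SAP wording and a few lines of code. No extra samples, patients or changes to conduct are needed. The wording should be fixed before unblinding, so that the handling of 0 h is not chosen with results in view.

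### Does an open list of secondary biomarkers, with every test read at unadjusted p < 0.05, call for a change to the plan?

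*Combined protocol and SAP*

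**What the plan says.** The Outcomes paragraph sets a single primary outcome: "The primary outcome will be coenzyme Q10 plasma levels". The statistical analysis plan adds one main time-point: "Our primary time-point of interest will be 24 hours after administration of the study drug". Below that sits the secondary tier: "Secondary outcomes will include additional biomarker measurements (including neuron specific enolase), oxygen consumption, and clinical outcomes (mortality and neurological outcomes". NSE is the only biomarker named there, and the wording does not close the list.

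The statistical analysis plan then gives a rule for all tests: "All hypothesis tests will be two-sided and a p-value < 0.05 will be considered significant". It mentions no multiplicity adjustment, no order of testing among the secondary outcomes, and no statement that secondary findings are exploratory. It also plans repeated measures models over 0, 24, 48 and 72 hours as a secondary analysis, without listing the outcomes they cover.

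Two further statements bear on the point. Under Treatment protocol, "the blood will be centrifuged and aliquoted into light-protected cryotubes and frozen". Under Randomization and blinding, "Patients, clinicians, and the research team will remain blinded throughout the full duration of the study".

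**The concern.** Each feature is common on its own; the combination draws attention. If the list is open, samples are stored and any p below 0.05 counts as significant, a reader of the plan cannot tell how many biomarkers will stand behind one reported result. An assay could be added late and its p-value presented like any other.

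The secondary tier also matters in this trial. The primary outcome is the plasma level of the substance being given, so evidence that the patient is affected has to come from NSE, oxygen consumption, mortality or neurological outcome. A chance finding there could be taken for a signal of effect.

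**Working it through.** **Reproducing a figure from the plan.** There is none to reproduce. The documents give no sample size, power, number of tests or family-wise error rate. The only stated input is the per-test level, two-sided 0.05.

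**Inputs.** Per-test level 0.05 (statistical analysis plan). Four named secondary items: NSE, oxygen consumption, mortality, neurological outcome (Outcomes). Assumed: one test per item, all nulls true, and a common correlation between test statistics of 0, 0.5 or 0.8. A larger case assumes five further biomarkers, giving 4 + 5 = 9 tests.

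**Formulas.** For k independent tests, the chance of at least one p < 0.05 is 1 − 0.95^k. The chance of at least one in favour of ubiquinol is 1 − 0.975^k. For correlated tests the same probabilities come from equicorrelated normal statistics, integrated over one shared factor.

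- k = 4, independent: 1 − 0.95^4 = 0.185; favouring ubiquinol, 1 − 0.975^4 = 0.096.
- k = 9, independent: 1 − 0.95^9 = 0.370; favouring ubiquinol, 1 − 0.975^9 = 0.204.

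| Tests | Direction | Correlation 0.8 | 0.5 | 0 |
|---|---|---|---|---|
| 4 | either | 0.114 | 0.156 | 0.185 |
| 4 | favouring ubiquinol | 0.057 | 0.078 | 0.096 |
| 9 | either | 0.166 | 0.269 | 0.370 |
| 9 | favouring ubiquinol | 0.083 | 0.135 | 0.204 |

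One test per item may be too few, because the repeated measures models could add a second test for some outcomes. If NSE and oxygen consumption each had one more, k = 6 and the either-direction figures become 0.138, 0.208 and 0.265.

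**What the usual remedy would alter.** Closing the list and calling secondary results unadjusted and hypothesis-generating leaves 0.05 per test in place. For any given k, every entry in the table is the same before and after. Only a formal adjustment would move them: Bonferroni with k = 4 uses 0.05/4 = 0.0125 per test and gives 1 − (1 − 0.0125)^4 = 0.049. Adjustment of secondary outcomes is not obligatory in a phase II trial, and the concern does not ask for it.

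**Primary comparison.** One outcome at one primary time-point is a family of one, with error 1 − 0.95^1 = 0.05, however many secondary assays are run. The plan does not name the model for that comparison, which is a separate matter.

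**The stored-sample route.** Plasma measurements of coenzyme Q10 and NSE need processed blood from the scheduled draws, so freezing aliquots fits the planned assays. The documents describe no banking for later use and no retention period. The research team is blinded for the whole study, so assays chosen in that time cannot be picked by treatment result. What happens to any remaining aliquots afterwards is neither stated nor excluded.

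**The case for a change.** The strongest case for acting is that the request is modest. It asks for a list of assays before unblinding, a post hoc mark on anything added later, and one sentence on interpretation. Secondary p-values stay. An open list would be tolerable if the plan said how secondary results are read, and a flat 0.05 would be tolerable if the list were closed; here neither holds. The threshold sentence covers all tests and so does not itself separate primary from secondary, and blinding is promised only for the duration of the study.

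The factual part stands. The list is open, the intended reading is not written down, and from the plan alone a reader cannot count the planned assays. Listing them would be good practice.

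The step to a needed change does not stand. The threshold sentence is a per-test convention and does not say that a significant secondary result will be claimed as an effect. The ranking is set in the Outcomes paragraph and by the choice of a primary time-point. Late growth of the list from frozen samples is an inference, since no such plan is described.

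**Conclusion.** No change to the plan is needed. It omits a detail and states no wrong rule: the primary comparison keeps its 5% level, the secondary outcomes are labelled as secondary, and no efficacy decision depends on them. The suggested wording would leave every test and p-value as planned. It would record a reading that analysts of a single-center phase II trial with a drug-level primary outcome would ordinarily adopt. The sponsor may name the assays before unblinding and mark later ones as post hoc, but this is an optional clarification.

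The percentages, 11% to 19% for four tests and 17% to 37% for nine, illustrate unadjusted testing in general. They rest on assumed test counts, assumed correlations and all nulls being true, so they do not measure a defect of this plan. The conclusion assumes that the report will state which biomarkers were assayed and will present secondary results as secondary. A claim of benefit resting on one unadjusted secondary p-value would be a fault of that report, and nothing in the plan provides for it.
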